Objectives	
Primary objective: To assess organ specific phenotypes and biomarker profiles to characterize specific cardiovascular, pulmonary, renal and other abnormalities and their role in functional status, quality of life and prognosis in COVID-19 survivors.
 
Specific objectives:
 
(1) To characterize cardiac and extracardiac phenotypes in COVID-19 survivors (compared to control subjects without a history of symptomatic COVID-19), and their relationship with:
(a) quality of life; (b) functional status; (c) aerobic capacity; (d) prognosis.(2) To determine if the severity of COVID-19 is associated with measures of organ-specific structure and function after recovery.(3) To perform prospective follow-up of the cohort for the development of death, heart failure-related hospitalizations, and other adverse cardiovascular outcomes.(4) To establish a biorepository for future discovery.
Number of Subjects	200 COVID-19 survivors and 80 controls are expected to be enrolled at Penn Medicine.

CONFIDENTIAL

This material is the property of the University of Pennsylvania.

Main Inclusion and Exclusion Criteria	
Inclusion criteria:
 
• Subjects aged 18 years and older, male or female;• Prior diagnosis of COVID-19 (acute symptoms consistent with COVID-19, confirmed by PCR, serologic or rapid antigen test) for the COVID-19 survivors group, or no confirmed or suspected prior history of symptomatic COVID-19 for the control group at the time of enrollment. 
Exclusion criteria:
 
• Pregnancy at the time of the index COVID-19 episode or at the time of the first enrollment in the study; potential participants who become pregnant after the index COVID-19 episode will not be invited to participate until at least 3 months post-delivery. Inability to provide informed consent.• Known history of CVD (defined as HF, MI, coronary revascularization, serious arrhythmia, stroke, greater than moderate valvular heart disease, any cardiomyopathy, or PAD), glomerular disease or polycystic kidney disease prior to enrollment.• End stage kidney disease (ESKD; defined as requiring persistent renal replacement therapy or prior kidney transplant) prior to enrollment• History of chronic kidney disease (CKD) with eGFR <30 mL/min/1.73m² prior to enrollment. In participants without a history of CKD, a measurement of eGFR will not be required for enrollment.
--	---

CONFIDENTIAL

This material is the property of the University of Pennsylvania.

Study procedures	
• The phenotyping protocol will include brief questionnaires, a brief ultrasound examination, arterial tonometry, measurements of endothelial function, a 6-minute walk test, pulmonary function tests, Short Physical Performance Battery, impedance cardiography, blood, urine and breath condensate collection and 24-hour blood pressure monitoring. A subset of participants will be asked to complete a cardiopulmonary supine bike exercise test. All tests except for VO2 testing will be repeated at approximately 18-month intervals for a total of 3 tests
Statistical Methodology	Statistical techniques will include t-tests, linear regression models, mixed models, network analysis, pathway analysis, and machine-learning approaches. The relationship between phenotypic profiles and incident risk will be assessed using a combination of Cox regression, Poisson regression, and Kaplan-Meier survival analyses, as needed. Corrections for multiple comparisons will be performed with false discovery rate correction, Bonferroni correction, or principal-components analysis-based correction, as appropriate.
Data and Safety Monitoring Plan	The Investigators will be responsible for the data quality management and the ongoing safety of subjects.

CONFIDENTIAL

[figure not shown]
Background and Study Rationale

1 Introduction

A1. With the ongoing spread of coronavirus disease 2019 (COVID-19), there is a growing population of COVID-19 survivors. COVID-19 is a public health crisis. Severe acute respiratory syndrome coronavirus 2 (SARS-CoV-2), the virus responsible for the COVID-19 pandemic, is associated with a high risk of pneumonia and multiorgan dysfunction.¹⁻⁴ Despite containment and mitigation efforts, COVID-19 continues to spread. As the case fatality rate for COVID-19 is estimated at <1%,⁵ it follows that along with the pandemic increase of COVID-19 cases, there will be a marked increase of COVID-19 survivors in the general population.

A2. COVID-19 survivors may be at an elevated risk of major adverse cardiovascular events (MACE). Pneumonia is the prominent feature of COVID-19.¹ Over the last several years, we and others demonstrated that survivors of pneumonia (irrespective of etiology), instead of going back to their pre-infection baseline health trajectories, enter a trajectory of increased risk of MACE,⁶⁻²⁰ including new onset heart failure, myocardial infarction (MI), and stroke, as demonstrated in **Figure 1**. For example, we identified 591 pneumonia cases in the Cardiovascular Health Study (CHS) and 680 pneumonia cases in the Atherosclerosis Risk in Communities (ARIC) study.^{6,7} In CHS, 206 participants (35%) experienced a MACE during the 10 years after their pneumonia hospitalization. Of these, 104 (51%) experienced MI, 35 (17%) experienced stroke, and 67 (33%) experienced fatal coronary heart disease events. Between 91 days and 1 year following hospitalization, compared to matched controls, the HR for MACE was 2.10 (95% confidence interval [CI] 1.59-2.60); during the second year after hospitalization, the HR was 1.89 (95% CI 1.46-2.33). We found similar risk of MACE following pneumonia hospitalization in ARIC. In both cohorts, we observed that the risk associated with pneumonia was markedly higher than the risk associated with traditional risk factors (diabetes, hypertension, and smoking, among others).

[figure not shown]
Figure 1. Adjusted risk of myocardial infarction or stroke (left panel) and heart failure (independent of myocardial infarction; right panel) after hospitalization for pneumonia in the Cardiovascular Health Study. Adapted from Corrales-Medina et al. *JAMA*. 2015; 313(3):264-74 and Corrales-Medina... Chirinos JA. *Am Heart J*. 2015; 306-312.e6

CONFIDENTIAL

A3. There is a multifaceted pathophysiologic relationship between pneumonia and cardiovascular (CV) disease. As previously discussed,⁹ the pathogenesis of CV complications of acute pneumonia is complex, and involves systemic inflammation, endothelial dysfunction, increased arterial stiffness, abnormal arterial hemodynamics, abnormalities in coronary perfusion, and direct myocardial damage from a variety of factors. Importantly, some of these factors may result not only in acute complications, but also in long-term consequences for CV health. Moreover, systemic inflammation may persist for months after resolution of the acute event.²¹ Inflammatory processes govern the progression of atherosclerosis from fatty streaks to advanced atherosclerotic plaques and their complication and evolution into clinical CV events such as MI and stroke.²² Acute and chronic inflammation can lead to endothelial dysfunction, increase arterial stiffness and impair pulsatile arterial hemodynamics (all of which can mediate CV risk independently of atherosclerosis).²³ Even in the absence of systemic inflammation, progression of vascular and target organ damage initially sustained during acute pneumonia events could mediate long-term CV risk.

Figure 2. Conceptual model: Overview of the association of COVID-19 with microvascular and macrovascular disease, kidney dysfunction, and cardiovascular events

A4. Because of its unique pathophysiology, COVID-19 may distinctly predispose patients to chronic pulmonary disease, MACE and micro- and macrovascular damage/dysfunction. COVID-19 may predispose patients to particularly elevated risk of CV damage due to its distinctive proinflammatory and prothrombotic pathophysiology (Figure 2). In the acute phase, COVID-19 is associated with a relatively high incidence of thromboembolic events, MI, stroke, and severe arrhythmias.^{24,25} Hyperinflammation and micro- and/or macrovascular thromboembolic or *in situ* thrombotic complications have been observed acutely and sub-acutely in COVID-19 in the vasculature of the lungs, spleen, brain, gut, kidneys, and periphery,²⁶⁻²⁸ even with therapeutic anticoagulation.²⁸ Thromboses have been identified several weeks following critical illness, suggesting a protracted duration of pro-thrombotic risk post-hospitalization. Importantly, viral inclusion bodies within endothelial cells and sequestered mononuclear and polymorphonuclear cellular infiltration of the endothelium are seen in COVID-19, along with evidence of endothelial cell apoptosis.³⁷ This is consistent with the presence of endotheliitis, which could lead to acute and chronic vascular dysfunction resulting in target organ dysfunction and increased CV risk. Thromboembolic disease may also result in reduced aerobic capacity and exercise intolerance due to potentially chronically effects on the pulmonary vasculature.^{29,30}

CONFIDENTIAL

Furthermore, studies demonstrate the potential for persistent restrictive lung disease several months following recovery from acute COVID-19³¹ and possible risk of pulmonary fibrosis.³²

A5. COVID-19 may also predispose patients to clinical and subclinical kidney target organ damage, which could mediate long-term CV risk. Hospitalization for pneumonia of all causes is associated with a persistently elevated risk of subsequent CKD.^{33,34} For example, in a Swedish cohort of 284,198 men born from 1952-1956, there were 5,822 initial pneumonia episodes observed over 37 years of follow up.³³ In the year following the first episode, pneumonia was associated with a 14.5-fold (95% confidence interval [CI] 10.41-20.32) elevated hazard of incident CKD; there was a 5.2-fold (95% CI 3.91-6.93) elevated hazard of incident CKD in the first five years following pneumonia. COVID-19 is particularly associated with a high incidence of acute kidney injury.^{35,36} The mechanisms of acute kidney injury in COVID-19 seem to be largely immune- and coagulopathy-mediated, including marked interstitial inflammation, microangiopathy with peritubular and glomerular erythrocyte aggregation and fibrin thrombi, endothelial damage, and tubular necrosis.^{35,37} The presence or severity of acute kidney injury is often missed in hospitalized patients, and many patients may have subclinical kidney injury that is not identified by typical measurements (i.e. creatinine-based eGFR) during hospitalization.^{38,39} Even among individuals without evidence of acute or persistent kidney damage while hospitalized, the hyperimmune and coagulopathic mechanisms of COVID-19 may predispose COVID-19 survivors to an elevated risk of subsequent decline in kidney function. Our group has preliminary data demonstrating a strong association of decline in kidney function with elevated 1- and 3-year risk of MACE, regardless of baseline kidney function (see **A8. Preliminary Data**). Thus, decline in kidney function among COVID-19 survivors may be an important mediator of future CV risk in these patients.

A6. Several interrelated mechanisms of COVID-19 may be linked to acute multiorgan dysfunction and intermediate- and long-term target organ damage in COVID-19 survivors. In comparison to other bacterial and viral pneumonias, inflammation and hypercoagulability in COVID-19 may be related to its unique interaction with the renin-angiotensin system (RAS). Angiotensin-converting enzyme 2 (ACE2), a counter-regulatory component of the RAS, facilitates SARS-CoV-2 entry into host cells in the respiratory tract.⁴⁰ ACE converts angiotensin I (Ang I) to Ang II, which acts on the Ang II type 1 receptor (AT₁R), resulting in vasoconstriction, sodium and fluid retention by the kidney, oxidative stress, inflammation, fibrosis, and impaired fibrinolysis.^{41,42} In direct opposition to the cascade of physiological effects of the ACE/Ang II pathway, the net effect of the ACE2/Ang-(1-7) pathway is vasodilation and anti-inflammation. ACE2 hydrolyzes Ang II, converting it to Ang-(1-7). The conversion of Ang II to Ang-(1-7) diminishes the availability of Ang II to bind AT₁R, forestalling the vasoconstrictive, proinflammatory, and prothrombotic effects of AT₁R activation.⁴¹⁻⁴⁵ Additionally, Ang-(1-7) acts on the Mas receptor, resulting in vasodilation, natriuresis, and a reduction in oxidative stress and inflammation.^{46,47} Collectively, Ang-(1-7) counteracts the pro-inflammatory and pro-fibrotic effects of Ang II in the heart and kidneys.^{48,49} In animal models, unopposed Ang II in the setting of diminished ACE2 upregulated inflammatory cytokines interferon- γ , interleukin-6, and monocyte chemoattractant protein-1, and increased phosphorylation of extracellular signal-regulated protein kinase (ERK)1/2 and c-Jun N-terminal kinase (JNK)1/2 signaling pathways.⁵⁰ Furthermore, AT₁R activation by Ang II has pro-thrombotic effects, including enhanced platelet activation and impaired fibrinolysis, resulting in hypercoagulability.^{44,51,52} Ang II also stimulates plasminogen activator inhibitor-1, further promoting thrombus production.⁴² The pro-thrombotic effects of Ang II are downregulated by ACE2-mediated conversion into Ang-(1-7) and subsequent Ang-(1-7) signaling via MasR. ACE2 is more prominently expressed in the kidneys than in the lungs, and direct viral invasion of the kidneys may promote systemic abnormalities in RAS activity.^{53,54} Dysregulation of this pathway may contribute to the hyperinflammation, hypercoagulability, and endothelial dysfunction in COVID-19, and may mediate both acute and long-term target organ CV and kidney damage.^{55,56}

CONFIDENTIAL

A7. The incidence, severity, and mechanisms of enduring CV effects of COVID-19 are unknown, and urgently require prospective, systematic evaluation. The current proposal aims to prospectively evaluate the natural history of cardiovascular and kidney disease in COVID-19 survivors, and to identify risk factors for adverse mid- and long-term outcomes in these patients. Most studies evaluating COVID-19 hospitalizations rely upon administrative datasets, and are thus prone to misclassification of outcomes, unmeasured confounding, and confounding by indication for testing (e.g., those with underlying comorbidities are more likely to undergo frequent testing, whereas those without underlying comorbidities may not undergo follow-up testing at all). Administrative and retrospective studies also rely upon patients receiving all of their care within the same health system and do not adequately account for outmigration (e.g., due to change in insurance or change in geographic location) or loss to follow up, which may be exacerbated in the current setting due to high rates of unemployment and other economic pressures surrounding the COVID-19 pandemic. Administrative studies will also lack detailed, prospective, quantitative assessment of vascular function, a likely important mechanistic contributor to MACE in these patients. Moreover, to the degree that COVID-19 is a new disease and the mechanisms that may mediate its relationship with subsequent CV risk are unknown, it is essential to couple a careful assessment of incident CV events with deep mechanistic phenotyping of vascular and renal structure and function. Our team is experienced with these approaches and has been applying them in other settings (most notably, pneumonia of all cause, heart failure (HF) with preserved ejection fraction, and CKD). Our team also has a track record of translation of mechanistic phenotypes to the testing of novel candidate therapies. We aim to apply our experience and skills in the most expeditious fashion to contribute to a better understanding of intermediate- and long-term CV risk in the rapidly growing population of COVID-19 survivors.

2 Study Objectives

Primary objective: To assess organ specific phenotypes and biomarker profiles to characterize specific cardiovascular, pulmonary, renal and other abnormalities and their role in functional status, quality of life and prognosis in COVID-19 survivors.

Specific objectives:

- (1) To characterize cardiac and extracardiac phenotypes in COVID-19 survivors, and their relationship with: (a) quality of life; (b) functional status; (c) aerobic capacity; (d) prognosis.
- (2) To determine if the severity of COVID-19 is associated with measures of organ-specific structure and function after recovery.
- (3) To perform prospective follow-up of the cohort for the development of death, heart failure-related hospitalizations, and other adverse cardiovascular outcomes.
- (4) To establish a biorepository for future discovery.

3 Investigational Plan

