4.1 Data analysis plan

To characterize cardiac and extracardiac phenotypes in COVID-19 survivors, we will use latent class analysis with finite mixture modeling to classify individuals into mutually exclusive and exhaustive subgroups, maximizing within-group similarities and between-group differences on the basis of baseline covariates ¹⁰⁹⁻¹¹². Latent class models will be compared across successive numbers of subgroups and the optimal number of groups will be determined using the parametric bootstrap likelihood ratio test, Akaike's Information Criterion, Bayesian Information Criterion, and sample-size adjusted BIC ^{113,114}. We will use other clustering methods for corroboration of our identified phenotypes, including Gaussian mixture models via the expectation–maximization algorithm ⁷⁹, and consensus clustering ¹¹⁵ to evaluate the stability of the discovered clusters. Descriptive statistics will compare patients across phenotypes using Student's t-test, Wilcoxon rank sum, or Chi-square test, as appropriate. We will then assess for differences in quality of life and functional status across phenotypes using multinomial logistic regression. We will separately analyze the trajectory of each of the quantitative measures of vascular health and kidney function using mixed effects growth curve models.¹¹⁶ Where necessary, we will supplement these analyses with marginal models estimated by generalized estimating equations.¹¹⁷ We will assess for varying length of follow-up among subgroups to evaluate for any potential bias this may introduce. We will assess for effect modification by sex and race due to potentially important differences in COVID-19 outcomes¹¹⁸⁻¹²⁰ and trajectory of vascular and kidney health.^{121,122} We will also use methods that classify participants according to their vascular and kidney health trajectories, using each individual parameter and extended to multiple parameters. We will use the latent class mixed effects model^{123,124} to analyze trajectories of vascular and kidney health within our study population. The latent class mixed effects model introduces an additional variable to represent class membership, which can be modeled through a multinomial logistic regression.

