4.2 Power calculations

We will enroll 200 COVID-19 survivors following recovery from their hospitalization and 80 controls. For analyses of trajectory of vascular and kidney health, accounting for multiplicity across multiple outcome parameters at an alpha at 0.0025, ¹³⁰ we will have >80% power to observe, for example, a mean difference in slope of PWV of 0.8 m/s and eGFR of 4 mL/min/1.73m² per 18-month visit interval across COVID-19 survivors and non-COVID-19 controls, assuming intraclass correlation coefficient of 0.1 and 20% loss to follow-up.¹³¹ For determining the association of hospitalization severity with risk of MACE, the most conservative endpoint in the study, we assumed a cumulative event rate of 5% over 5 years of follow-up ^{6,7}, accounting for our exclusion of individuals with prior CVD. Assuming a retention rate of 80%, we will have 90% power at an alpha of 0.05 to detect a regression coefficient of 0.9 in the Cox model ^{132,133}. In analyses evaluating for sub-phenotypes and risk factors for MACE, using a conservative Bonferroni approach to account for multiplicity across several risk factors ¹³⁰, we will have over 90% power at an alpha of 0.005 to detect a regression coefficient of 0.9 for every standard deviation difference in parameter. Power calculations were performed using PASS16 ¹³⁴.

5 Study Administration, Data Handling, and Record Keeping

All information obtained as part of protocol will be maintained in locked research files. Electronic data will be stored in a password secured database (REDCap). This database will be available only with secure high-level password protection to safeguard the privacy of the participants. Any source documents for each patient involved in the protocol, other than the patient's electronic medical chart, will be maintained in a centralized, secured location.

Data collected will contain protected health information (PHI) including name, date of birth, and medical record number. Information about study subjects will be kept confidential and managed according to the requirements of the Health Insurance Portability and Accountability Act of 1996 (HIPAA). Research data will be stored in a centralized, secure location (locked cabinets in the PI's research space).

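### Section 4.1 names Student's t-test and the rank sum test for comparing latent classes that may differ in size and spread and may number more than two; Welch's forms should be named instead (minor)

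*Combined protocol and SAP*

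**What the plan says.** - **Synopsis, Statistical Methodology.** It lists t-tests among the methods, without the variant or the comparison they serve: "Statistical techniques will include t-tests, linear regression models, mixed models, network analysis, pathway analysis, and machine-learning approaches". It also provides for multiplicity: "Corrections for multiple comparisons will be performed with false discovery rate correction, Bonferroni correction, or principal-components analysis-based correction, as appropriate".
- **Section 4.1, Data analysis plan.** This is the only place that names the Student's form, and it ties it to latent-class phenotypes: "Descriptive statistics will compare patients across phenotypes using Student's t-test, Wilcoxon rank sum, or Chi-square test, as appropriate". The number of classes is left open: "Latent class models will be compared across successive numbers of subgroups". Bootstrap likelihood-ratio and information criteria then decide. Quality of life and functional status are compared across phenotypes by multinomial logistic regression, and trajectories by mixed-effects growth curve models.
- **Synopsis, Number of Subjects.** "200 COVID-19 survivors and 80 controls are expected to be enrolled at Penn Medicine".
- **Section 4.2, Power calculations.** The powered survivor-control comparison concerns slopes, "accounting for multiplicity across multiple outcome parameters at an alpha at 0.0025". A level of 0.05 appears only for the Cox analysis of severity. No level is stated for any t-test, and neither an SD nor a class size is given.

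**The concern.** Student's t-test estimates one common variance. When group sizes differ, that estimate is dominated by the larger group. If the smaller group is the more variable, the standard error comes out too small and the test rejects too often. If the larger group is the more variable, the standard error is too large and the test loses power.

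Latent classes are exposed to both conditions. Nothing in the method makes them equal in size, and a class that collects abnormal profiles can easily be both small and widely spread. The index illness among survivors runs from never hospitalised to mechanically ventilated (section 3.6.1, severity score), so unequal spread is plausible, although the documents do not quantify it.

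Student's test and the rank sum test are also two-sample procedures. If three or more classes emerge, the list offers no overall test for a continuous variable.

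At stake is which variables are reported as separating the phenotypes. The issue covers every continuous variable compared, including those that did not help to form the classes.

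**Working it through.** The plan states no error rate, power or sample size for a t-test, so there is no figure of its own to reproduce.

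**Inputs**
- Survivors to be classified: 200 (synopsis).
- Class sizes 160 and 40: assumed, adding to 200.
- SD ratios 1.3, 1.5 and 2, in either direction: assumed.
- Two-sided 5%: assumed by convention.
- Normal data with equal means.

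**Formula.** The pooled variance is sp² = [(n1−1)s1² + (n2−1)s2²]/(n1+n2−2). The ratio of the standard error used to the true one is r = √{ sp²(1/n1+1/n2) / (s1²/n1 + s2²/n2) }. The true two-sided size is approximately 2[1 − Φ(t_crit × r)], with t_crit = 1.972 on 198 degrees of freedom.

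**Worked case: 160 with SD 1, 40 with SD 2**
- sp² = (159×1 + 39×4)/198 = 1.591.
- Squared standard error used: 1.591 × (1/160 + 1/40) = 0.0497.
- True squared standard error: 1/160 + 4/40 = 0.1063.
- r = √(0.0497/0.1063) = 0.684.
- Effective critical value: 1.972 × 0.684 = 1.349.
- True size: 17.7%.

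**All cases at 160:40** (simulation: 100,000 data sets each)

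| More variable class | SD ratio | Student's, formula | Student's, simulated | Welch, simulated |
|---|---|---|---|---|
| Neither | 1 | 4.9% | 5.0% | 5.0% |
| Smaller (40) | 1.3 | 9.2% | 9.3% | 5.0% |
| Smaller (40) | 1.5 | 12.0% | 12.1% | 5.1% |
| Smaller (40) | 2 | 17.7% | 17.7% | 4.8% |
| Larger (160) | 1.3 | 2.1% | 2.2% | 5.0% |
| Larger (160) | 1.5 | 1.3% | 1.3% | 4.9% |
| Larger (160) | 2 | 0.4% | 0.5% | 5.0% |

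**Dependence on the split (formula).** With a milder 140:60 split and the smaller class more variable, the size is 9.2% at ratio 1.5 and 12.3% at ratio 2. With 100:100 it stays at about 5% for every ratio.

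**Does multiplicity correction repair this?** Take a threshold of 0.0025, borrowed from section 4.2 only as an example of a corrected level. At 160:40 with the smaller class more variable, Student's true size is 1.6% at ratio 1.5 and 3.6% at ratio 2 (formula). That is 0.016/0.0025 ≈ 6 times and 0.036/0.0025 ≈ 14 times nominal. Welch simulates at 0.27% and 0.22%. Stricter thresholds therefore make the relative error larger.

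**Do rank tests repair it?** Under the same conditions (ratio 2, smallest class more variable, 20,000 data sets), the rank sum test at 160:40 rejects about 11%. With classes of 100/60/40 or 120/40/40, Kruskal-Wallis rejects about 8% in both, ordinary ANOVA about 12%, and Welch's ANOVA 5.0% and 4.7%.

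**Price when variances are equal.** At 160:40, with the mean difference set for 80% power, Student's test has 80.1% and Welch's 79.2%.

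**The case against.** The strongest reply is that this is a descriptive table with the choice of test left to judgement, and that several stronger readings go beyond the text. Most of that is right.

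- **Student's test for survivors versus controls.** A reader might infer that the 200 versus 80 contrast will use a pooled t-test. The documents do not say so. The synopsis names no variant, Welch's test is itself a t-test, section 4.1 ties Student's to phenotypes, and the powered survivor-control comparison is of slopes, for which section 4.1 plans mixed models.
- **A real error rate of 1% to 18% instead of 5%.** This range would join two different scenarios, 200:80 and 160:40, each with an assumed SD ratio of 2 and in opposite directions. Taken separately, and allowing either direction, 200:80 gives about 1% to 13% and 160:40 about 0.4% to 18%. With equal SDs or equal groups the rate is 5%. None of these is a property of the plan.
- **Unadjusted pairwise testing.** Uncorrected all-pairs tests would give at least one false difference with probability of about 12% to 14% for three classes and 20% to 26% for four. The synopsis promises a correction, so these figures cannot be charged to the plan.
- **No overall test at all.** Chi-square handles any number of classes, and multinomial regression permits an overall test for quality of life and functional status. The gap is confined to continuous variables in the descriptive comparison.

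Two parts of the reply fail. Leaving the choice to judgement selects only among the listed tests, and none of them compares means under unequal variances or compares a continuous variable across three or more classes. The promised correction operates on p-values that it takes to be valid, and so cannot repair them.

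**Conclusion.** The point holds as a minor one. Section 4.1 names a variance-pooling, two-sample test, and a two-sample rank test, for classes whose number, sizes and spreads are unknown. The size of the effect is conditional: at a nominal 5% with assumed classes of 160 and 40, Student's true level lies between about 0.5% and 18% for SD ratios up to 2, depending on which class is the more variable, while Welch's stays near 5%. These figures rest on normal data and on class sizes, SD ratios and a test level that the documents do not give. They should be read as showing the direction and possible scale of the error, and not as a forecast for this study. No stated sample size, power figure or powered comparison depends on this step.

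**What to change.** - **Section 4.1, two classes:** replace Student's t-test with Welch's t-test.
- **Section 4.1, three or more classes:** name Welch's ANOVA as the overall test for continuous variables, followed by pairwise Welch tests under the multiplicity correction already planned (for example Bonferroni, or Holm).
- **Do not offer Kruskal-Wallis or the rank sum test as the remedy for unequal spread**, because both are affected by it. They may stay for ordinal or strongly skewed variables, with that limit stated.
- **Synopsis:** where t-tests are used for survivors versus controls, specify the Welch form.

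The cost is a few words in the plan and, if variances turn out equal, about one percentage point of power (80.1% against 79.2% in the case above). The change does not make tests of the class-forming variables themselves meaningful; that is a separate matter.
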